Potential enrollees will be provided a simple questionnaire regarding dietary habits. This will help the researchers understand individuals' nutritional intake, more specifically vitamin D sources. They will also be provided an informative page on vitamin D function and treatment for deficiencies. During the physical, each subject will have blood drawn and baseline serum 25(OH) vitamin D3 will be recorded. Supplemental vitamin D3 treatment will be given in 50,000 IU dosages once a week for 8 weeks following the initial examination. The prescription will be: Vitamin D3 50,000 IU oral capsule take 1 pill per week for 8 weeks. Subjects receiving supplemental treatment will then have vitamin D3 levels checked again at 8 weeks to ensure serum levels have risen. These values will be recorded. Should serum levels of vitamin D3 remain below the target value of 30 ng/mL, these subjects will be treated again following the same protocol as the primary treatment to ensure the levels rise. The subjects will then be followed throughout the course of the season, including all training activities, practices, and games.

Both deficient and normal subjects will be re-tested in January upon return from winter break. Subjects showing serum 25(OH) vitamin D3 levels below normal will be given supplemental treatment of 50,000 IU dosages once a week for 8 weeks. These subjects may have new or recurring deficiencies. Serum levels will be checked again following the end of treatment to ensure levels have risen. Any subject that was within normal ranges in the fall sports season that drops to deficient ranges will be treated with the same dosage as the primary treatment. Should their serum vitamin D3 levels fail to rise after 8 weeks, a secondary treatment will be administered following the same protocol as the primary treatment.

Throughout the seasons, any subject complaining of pain or injury to the lower extremity will undergo examination by the physician in order to positively diagnosis the injury. Each positively identified stress fracture will be recorded for that subject, and the appropriate treatment and rehabilitation will ensue. The lower extremity will be defined as any portion of the femur, tibia, fibula, and bones of the foot and ankle. Should an injury occur that does not

directly relate to a stress fracture or the lower extremity, the subject will remain in the study. However, these subjects will be included in a separate analysis.

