Other than normal activities required for each sport, the main risk to each subject primarily involves taking blood samples. Although sampling is routine, there will still be risks of bleeding, bruising, dizziness, and possible infections. Allowing only trained individuals to take blood samples will minimize these risks. Any injury that occurs during a sports event or training activity will be handled accordingly by one of the physicians or athletic trainers on site. All injuries, regardless of nature, will be recorded per subject.

Blood samples will be tested for 25(OH) vitamin D levels using the order (Vitamin D 25-OH, Calcifediol Request). The data will be kept for each subject, day of recording, and level on an Excel spreadsheet. Any stress fracture reported will be listed on the same spreadsheet, along with the date of occurrence and severity, per subject.

Each team's athletic training staff will administer one vitamin D capsule to each team member once a week before a scheduled meeting or practice. This will help ensure every athlete takes the proper dosage, no dosages are skipped, and every week is accounted for. Athletes may still have decreased levels after the first course, and a second round of 8-week treatment will be administered. Should the second round of treatment fail to elevate vitamin D levels, the January test will confirm and treatment will continue. As many students leave to visit family during break, it will be rather difficult to monitor every athlete's levels during this timeframe.

Retrospective: The retrospective portion of the study will involve review of athletes of the same sports teams and inclusion/exclusion criteria from seasons up to four years ago. Review of previous athlete information will be drawn from electronic records kept by the athletic training staff, both electronic and hand-written records kept by the orthopedic staff, and any lab records retained at Palmetto Health. The information that will be obtained will include athlete demographics, their respective sports, stress fracture occurrences, and vitamin D levels if this was noted. The time period for the retrospective chart review will be from January 2010 through August 2015. The rate of stress fracture occurrence will be compared to the prospective treatment phase. It is important to note that individuals in the retrospective analysis will not have personal information reported, as the main purpose is to determine a baseline stress fracture rate.

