Analysis of the historic group will follow similar protocol as the recruitment of new subjects. Information from previous subjects will include including gender, age and sports team information. Additional information obtained will include stress fracture occurrence(s) and location, and vitamin D levels (if recorded).

h) Data and Specimen Banking

Data for each enrolled subject will consist of name, age, gender, ethnicity, and sports team. Any personal or private information collected will only be used during data analysis. This may contain information regarding menstruation, dietary habits, and previous pregnancies. Names and private information of subjects will not be released outside of personnel directly attached to the study, and they will not be included in the final study publication. Serum 25(OH) vitamin D levels for each subject will be recorded at the initial examination and 8 weeks following the beginning of treatment. Every injury diagnosis will be recorded per individual. There will be no blood sample banking after vitamin D levels are determined.

i) Statistical Analysis

Sample Size Justification

A power analysis was performed using PASS 2008 software on the research aim to compare the proportion of athletes that experience a stress fracture in those with normal vitamin D levels (either normal at baseline or treated by supplementation) compared to four previous years when this approach was not used. You can see that if the proportion of athletes experiencing stress fracture in the control group is 10%, then if the true reduction in the treated group was to 4% or less, we would have greater than 80% chance (power) in this study to achieve statistical significance in a test of the two proportions.

Two Independent Proportions (Null Case) Power Analysis

Numeric Results of Tests Based on the Difference: P1 - P2

H0: P1-P2=0. H1: P1-P2=D1<>0. Test Statistic: Z test with pooled variance

Power	Sample	Sample	Prop H1	Prop	Diff if H0	Diff if H1	Target Alpha
	Size Grp 1	Size Grp 2	Grp 1 or Trtmnt	Grp 2 or Control			
	N1	N2	P1	P2	D0	D1	
0.9946	200	800	0.0200	0.1000	0.0000	-0.0800	0.0500
0.9509	200	800	0.0300	0.1000	0.0000	-0.0700	0.0500
0.8220	200	800	0.0400	0.1000	0.0000	-0.0600	0.0500
0.6188	200	800	0.0500	0.1000	0.0000	-0.0500	0.0500
0.4048	200	800	0.0600	0.1000	0.0000	-0.0400	0.0500
0.2337	200	800	0.0700	0.1000	0.0000	-0.0300	0.0500
0.1224	200	800	0.0800	0.1000	0.0000	-0.0200	0.0500

Statistical Analyses

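### Aim 1 compares fractures found by examination and logging in 2015-16 with fractures taken from old records, and no common case definition is stated for the two periods

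*Combined protocol and SAP*

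**What the plan says.** **2015-16 cohort.** Under g) Procedures Involved, Prospective, the rule is that "any subject complaining of pain or injury to the lower extremity will undergo examination by the physician" so that the injury can be diagnosed, and "Each positively identified stress fracture will be recorded for that subject". The same section puts each fracture, with its date and severity, on the study spreadsheet. It also defines the sites: "The lower extremity will be defined as any portion of the femur, tibia, fibula, and bones of the foot and ankle". Injuries unrelated to a stress fracture or to the lower extremity go to a separate analysis. Section m) Withdrawal of Subjects withdraws athletes who fracture a bone outside that definition and keeps withdrawn athletes out of the final analysis. Section 8) Risks to the Subjects likewise leaves fractures above the lower extremities out of the analysis.

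**Control years.** Under g) Procedures Involved, Retrospective, the work is a "review of athletes of the same sports teams and inclusion/exclusion criteria from seasons up to four years ago". The sources are given as follows: "Review of previous athlete information will be drawn from electronic records kept by the athletic training staff", then "both electronic and hand-written records kept by the orthopedic staff", and any retained laboratory records. On the outcome the text says "Additional information obtained will include stress fracture occurrence(s) and location". It gives no bone list, no confirmation standard and no rule for fractures at other sites. The statement that the historic group is handled similarly refers to recruitment, not to diagnosis.

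**Analysis.** Section i) Statistical Analysis, Aim 1, tests the two proportions directly and gives a 95% confidence interval. An exploratory logistic model adds sport and gender. Neither step addresses how fractures were found or which sites count.

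**The concern.** Ascertainment changes at the same moment as the intervention, so any difference it makes is fully confounded with period. Adjustment for sport and gender cannot remove it.

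There are two separate mechanisms:

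- **Case finding.** Examining every complaint and logging the result at the time may find fractures that a search of old records would miss. This raises the 2015-16 proportion relative to controls. It can hide a benefit or suggest harm.
- **Sites counted.** If other-site fractures are left out in 2015-16 but counted among controls, the control proportion is raised relative to 2015-16. This can create an apparent benefit.

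The sample size rests on this comparison with earlier years. If the site rule for controls stays open, it may be settled after the fracture counts are known.

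**Working it through.** **Inputs from the plan** (section i, Sample Size Justification): 200 athletes in 2015-16, 800 controls, control proportion 10%, treated proportion 4%, two-sided alpha 0.05, pooled-variance Z test, stated power 0.8220.

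**Inputs assumed:** the share of fractures that chart review captures, and the share of fractures outside the listed bones. The documents give neither, so ranges are used.

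**1. Reproducing the plan's figure.** Power = Φ[(|p1 − p2| − 1.96·s0)/s1], with s0 = √[p̄(1 − p̄)(1/200 + 1/800)] and s1 = √[p1(1 − p1)/200 + p2(1 − p2)/800].

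- p̄ = (200 × 0.04 + 800 × 0.10)/1000 = 0.088
- s0 = 0.0224 and s1 = 0.01745
- (0.06 − 1.96 × 0.0224)/0.01745 = 0.92, so power = 0.822, as stated

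The other six rows of the table agree to within 0.002. The calculation takes both recorded proportions to be the same outcome, captured equally well.

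**2. Incomplete charts.** The true proportions are 10% and 4%, all 2015-16 fractures are found, and the recorded control proportion is 0.10 × capture. Power uses the formula above. The false-increase column takes a true proportion of 10% in both periods and sums exact binomial probabilities over the upper rejection region of the same test.

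| Capture (assumed) | Recorded control | Power at true 10% vs 4% | Chance of a false increase, no true effect |
|---|---|---|---|
| 100% | 10.0% | 0.822 | 2.9% |
| 95% | 9.5% | 0.756 | 4.6% |
| 90% | 9.0% | 0.679 | 7.3% |
| 80% | 8.0% | 0.499 | 16.1% |

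**3. Other-site fractures left out in 2015-16 only, no true effect.** The result depends on which proportion is held at 10%, so both versions are shown. With no bias, the exact chance of a false benefit is 2.1%.

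| Other-site share (assumed) | Control held at 10% over all sites: 2015-16 vs control | False benefit | Listed-bone proportion held at 10%: 2015-16 vs control | False benefit |
|---|---|---|---|---|
| 10% | 0.10 × 0.90 = 9.0% vs 10% | 5.3% | 10% vs 0.10/0.90 = 11.1% | 5.7% |
| 20% | 0.10 × 0.80 = 8.0% vs 10% | 11.9% | 10% vs 0.10/0.80 = 12.5% | 14.7% |

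**4. Both together.** With the listed-bone proportion at 10% and no true effect, the recorded control proportion is 0.10 × capture/(1 − other-site share).

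- Capture 90%, share 10%: 0.10 × 0.90/0.90 = 10%. The tails return to 2.1% and 2.9%, as with no bias.
- Capture 80%, share 10%: 0.10 × 0.80/0.90 = 8.9%. The chance of a false increase is 8.0%.
- Capture 90%, share 20%: 0.10 × 0.90/0.80 = 11.25%. The chance of a false benefit is 6.3%.

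The sign of the net bias therefore depends on two quantities that the documents do not supply.

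**The case against.** The strongest reply has four parts.

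- **The site rule may apply to controls.** The bone list is stated once, in the prospective text, but nothing says that it is withheld from controls. The Setting section frames the whole study around lower-extremity stress fractures, and location is abstracted for the historic group. This stands. A reader might infer that the list is applied only prospectively and that Aim 1 compares two different outcomes; the documents do not support that, because it turns silence into a rule. What remains is that the retrospective text carries over teams and eligibility but no case definition.
- **Earlier diagnoses may also be physicians' diagnoses.** Orthopaedic records are among the sources, and the documents do not say how complaints were handled before 2015. This also stands: more intensive case finding in 2015-16 is plausible, but neither its existence nor its size is established. Equally, nothing shows that earlier complaints led to the same examination or that the old records are complete.
- **Re-abstracting charts does not undo extra examinations.** Fractures found by more examination in 2015-16 would probably enter the same charts. This is correct and limits what the fix can do.
- **The biases may cancel, or may be conservative.** They can cancel, as step 4 shows, but nothing in the plan ensures it. Only the case-finding difference works against the treatment; the site difference would favour it.

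**Conclusion.** The point holds in this form: Aim 1 compares the same nominal outcome, ascertained differently in the two periods, with no common case definition stated and no analysis to handle the difference. The direction of the net bias is unknown.

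Its size rests wholly on assumed values. At 90% or 80% chart capture, power falls from 82% to 68% or 50%; even 95% capture takes it to 76%, below the 80% that the plan claims. An other-site share of 10%-20%, left out of 2015-16 only, raises the chance of a false benefit from 2.1% to about 5%-15%. These figures show sensitivity and are not estimates of the actual bias.

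A reader might also infer that the power table is wrong. It is not: it reproduces under its own inputs. This should be settled before control fractures are abstracted, because the site half is easily repaired and the case-finding half can at least be bounded.

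**What to change.** 1. In section i), Aim 1, pre-specify one case definition for both periods: a physician-documented stress fracture of the bones listed in the Prospective part of section g). Apply it to control fractures using the location already planned for abstraction.
2. State whether the removal of athletes with fractures at other sites applies to both periods, and apply the same rule to each in Aim 1.
3. For Aim 1, abstract 2015-16 from the same athletic-training and orthopaedic record systems, on the same form, as the control years. This assumes that those records are kept in the usual way that year. Report fractures known only from the study spreadsheet separately, and keep them for Aims 2 and 4.
4. Add a sensitivity analysis that repeats the Aim 1 comparison over assumed chart capture, for example 95%, 90% and 80%.
5. State as a limitation that these steps equalise definition, source and abstraction, but not how intensively athletes were examined.

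**Cost:** one more year of chart abstraction and a few sentences in the plan. Some 2015-16 fractures may not count in Aim 1.

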2. To compare the proportions of 2015-16 academic year student athletes experiencing stress fractures in the vitamin D insufficient or deficient group and the group with vitamin D levels ≥ 30 ng/mL.
3. In 2015-16 athletes, to explore associations between the TRIAD questionnaire risk factors and low baseline vitamin D levels.
4. In 2015-16 athletes, to explore associations between the TRIAD questionnaire risk factors and subsequent stress fractures.

Setting

This study will focus on athletes who are at a higher risk of lower extremity stress fractures. Specifically, this study will be looking at male and female athletes on the track, cross-country, soccer, and basketball teams at the University of South Carolina. During the pre-season physical of each student athlete, serum vitamin D levels will be taken and recorded. There will be a certified nurse to draw the blood samples. This will take place at the University of South Carolina Athletic Department and/or the Palmetto Health Lab at [name]. Potentially, every athlete of the given teams will be enrolled in the study unless they choose not to. Only subjects showing concentrations below 30 ng/mL, which is indicative of insufficient or deficient levels, will be provided supplemental treatment of 25-(OH) vitamin D. Every enrolled subject will be monitored for injury throughout the season. Any and all injuries will be positively identified, and any confirmed stress fractures will be recorded. Data from prospective seasons will be compared to an incidence percentage of athletes from previous seasons. Previous athletes did not receive any vitamin D treatment. These will be used as a control to determine if treatment affected the occurrence of stress fractures. All physicals and tests will be performed at the USC Sports Medicine clinic by the sports medicine staff.

Resources Available

Track, cross-country, soccer, and basketball are all considered high-risk sports due to the constantly high loads being placed on the lower extremities. Basketball is also included because

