Any subject that has consented and meets inclusion/exclusion criteria will be tested for serum vitamin D levels, and those individuals showing deficiency will be provided supplemental treatment in order to raise vitamin D levels to normal ranges. Individuals who do not show deficiency levels will be included in the study, but will not receive any treatment. These subjects will be added to an additional control group. There will be no payment for enrollment in the study.

b) Inclusion/Exclusion Criteria

Each individual who has given consent will have blood work tested. Should serum vitamin D levels be lower than 30 ng/mL, they will be included in the treatment group. Subjects with normal ranges will be included in the prospective control group. Both male and female athletes will be eligible to enroll. Any individual who currently has a stress fracture or is in the stage of recovering from a lower extremity musculoskeletal injury will be excluded from the study. Questionnaires will be provided in order to gather an understanding of diet, exercise regimen, and related lifestyle questions. Specifically, there will be a question regarding current vitamin D or other multivitamin supplement currently being taken, what the dosage is, and how often it is taken. Female athletes will be provided a separate questionnaire in regards to individual dietary habits and menstrual cycle.

c) Local Number of Subjects

The number of subjects in the study will be based on the number of individuals meeting the inclusion/exclusion criteria and provide written consent. They will be drawn from men's basketball, soccer, and track/field, and women's basketball, soccer, track/field, and cross-country. There will be no cutoff to the number of individuals accepted. Tentatively, there will be roughly 200 athletes enrolled in the study.

d) Study-Wide Number of Subjects

The number of subjects in the prospective portion of the study will be the number of qualified enrollees. This number may change, depending on the length of the study. Should it be necessary to extend the timeline, the study will enroll new subjects for the second season, but will still include them in the test group.

e) Study Timelines

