1. To compare the proportions of student athletes experiencing stress fractures during the 2015-15 academic year with the four previous years.

A large sample test of the difference in two independent proportions will be carried out, along with computation of 95% confidence interval on the difference between the two proportions. An exploratory logistic regression model will be built with stress fracture as the outcome, group (2015-16 versus the previous four years) as the major predictor variable and type of sport and gender as covariates.

2. To compare the proportions of 2015-16 academic year student athletes experiencing stress fractures in the vitamin D insufficient or deficient group and the group with vitamin D levels ≥ 30 ng/mL.

A large sample test of the difference in two independent proportions will be carried out, along with computation of 95% confidence interval on the difference between the two proportions. An exploratory logistic regression model will be built with stress fracture as the outcome, group (baseline vitamin D deficient versus normal baseline vitamin D level) as the major predictor variable and type of sport and gender as covariates.

3. In 2015-16 athletes, to explore associations between the TRIAD questionnaire risk factors and low baseline vitamin D levels.

Exploratory descriptive and inferential statistics will be carried out, including the building of linear and logistic regression models, looking for an association between the questionnaire items and baseline vitamin D levels (continuous and dichotomized).

4. In 2015-16 athletes, to explore associations between the TRIAD questionnaire risk factors and subsequent stress fractures.

Exploratory descriptive and inferential statistics will be carried out, including the building of logistic regression models, looking for an association between the questionnaire items and the subsequent occurrence of a stress fracture.

j) Data Management

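### The weekly capsule instruction to training staff is not limited to athletes below 30 ng/mL, so it conflicts with the rule that athletes with normal levels go untreated and serve as controls

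*Combined protocol and SAP*

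**What the plan says.** All references are to the combined protocol and SAP.

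- **Setting:** "Only subjects showing concentrations below 30 ng/mL, which is indicative of insufficient or deficient levels, will be provided supplemental treatment".
- **a) Recruitment Methods:** "Individuals who do not show deficiency levels will be included in the study, but will not receive any treatment".
- **b) Inclusion/Exclusion Criteria:** "Subjects with normal ranges will be included in the prospective control group".
- **g) Procedures Involved, on administration:** training staff are to "administer one vitamin D capsule to each team member once a week". The stated purpose follows: "This will help ensure every athlete takes the proper dosage, no dosages are skipped, and every week is accounted for".
- **g) Procedures Involved, on the January retest:** "Any subject that was within normal ranges in the fall sports season that drops to deficient ranges will be treated".
- **i) Statistical Analysis, item 2 (Aim 2):** the exploratory logistic model takes "group (baseline vitamin D deficient versus normal baseline vitamin D level) as the major predictor variable".

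**The concern.** The administration paragraph is the only place that gives weekly dosing to the team training staff. It describes the recipients as team members and athletes, and does not mention serum level or treatment group. Staff who worked from that paragraph alone would dose athletes whom the Setting section and section a) leave untreated.

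Two things would be at stake. The first is the comparator: section b) sets up the athletes with normal levels as a prospective control group, and Aim 2 compares their stress fracture proportion with that of the athletes below 30 ng/mL. If both groups took capsules, the Aim 2 contrast would no longer be between supplemented low-level athletes and unsupplemented normal-level athletes. The second is exposure: athletes with normal levels would receive a supplement that the treatment rule does not give them, and sections f) and 8) themselves list adverse effects of vitamin D supplementation and of excess dosing.

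**Working it through.** This is mainly a comparison of text. The one available calculation shows what the conflict does not touch.

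**1. Who receives capsules, section by section**

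| Section | Recipients |
|---|---|
| Setting | Only those below 30 ng/mL |
| a) Recruitment Methods | Those with deficiency; the others get no treatment |
| b) Inclusion/Exclusion Criteria | Below 30 ng/mL: treatment group; normal: control group |
| e) Study Timelines | Treated athletes, identified by deficient level, have the 8-week follow-up |
| g) dosing and retest text | Those low at baseline or in January, including baseline-normal athletes who fall |
| g) administration paragraph | Team members and athletes, no serum limit |

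The last row conflicts with the Setting section and with sections a) and b). No other text corrects it.

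**2. Does the context settle it?** Partly. The same paragraph goes on to speak of a first course and a second round, which only treated athletes have. On the other side, Prior Approvals uses the team-member wording for everyone on a team, while sections e) and g) have a narrower term, subjects receiving treatment, which the administration paragraph does not use. Resources Available says that other athletic trainers may assist, and requires of them only a basic familiarity with the protocol.

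**3. Effect on Aim 2.** The groups are set by baseline level, not by treatment received. The two proportions, their difference and its confidence interval can be computed whoever takes capsules. What changes is the meaning of the contrast:

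- Under the treatment rule, supplemented low-level athletes are compared with normal-level athletes, some of whom may be supplemented from January.
- Under the literal instruction, both groups are supplemented from the start.

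**4. Would a departure be visible?** The spreadsheet described in section g), the data list in section h) and the list in section j) cover serum levels, fractures and other injuries. None lists capsules given. The 8-week recheck is for treated athletes, so an athlete with a normal baseline would next be scheduled for testing in January.

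**5. Effect on the power calculation.** The powered comparison is Aim 1: the prospective athletes, normal at baseline or supplemented, "compared to four previous years when this approach was not used". Inputs from section i): N1 = 200, N2 = 800, P1 = 0.04, P2 = 0.10, two-sided alpha 0.05, pooled Z test.

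- Pooled proportion = (200 × 0.04 + 800 × 0.10) / 1000 = 0.088
- SE under H0 = √[0.088 × 0.912 × (1/200 + 1/800)] = 0.02240
- SE under H1 = √[0.04 × 0.96/200 + 0.10 × 0.90/800] = 0.01745
- Power = Φ[(0.06 − 1.96 × 0.02240) / 0.01745] = Φ(0.92) = 0.822

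The plan states 0.8220. The other six rows also reproduce to within 0.0014; the largest gap is in the last row, 0.1224 stated against 0.1210. Neither the group sizes nor the assumed proportions depend on how the capsule instruction is read. The plan gives no sample size, group split or effect size for Aim 2, so there is no Aim 2 figure to check.

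**The case against.** The strongest reply is that this is one loose noun. The paragraph is about supervised dosing, not eligibility. Its talk of a first course and a second round fits only treated athletes. The treatment rule is stated in the Setting section and in sections a) and b), and is assumed in sections e), g) and i). Providing January treatment for normal athletes who fall would make little sense if they were already being dosed. Section g) also refers to an attached flowchart, which is not in the available text and may show the allocation. Most of this stands: the intended reading is probably treated athletes only. It does not remove the need for a correction, because the written instruction to the staff who hand out capsules still lacks the limit.

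Three stronger readings are tempting, and the documents do not support them:

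- **Aim 2 has no untreated normal group.** That follows only if the instruction is carried out literally, which the context makes unlikely. Nor was a normal group untreated all year ever guaranteed, given the January rule.
- **Athletes who have not consented would be dosed.** Section b) ties testing to consent and group membership to the test result.
- **A definite number of athletes would be dosed wrongly.** The plan does not give the share of this population below 30 ng/mL, so any count would rest on an assumed share as well as on the least plausible reading.

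**Conclusion.** The contradiction is real and sits in an operative dosing procedure, so it should be corrected. It is a conflict of wording with a plausible benign reading, not proof that the control group will be lost.

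Its size is qualitative. If the instruction were followed as written, every baseline-normal athlete would be supplemented and Aim 2 would change meaning while remaining computable. If the treatment rule is followed, what remains is the smaller point that January treatment makes the normal group a mixed one, which the Aim 2 text does not describe. The Aim 1 power figures stand, although under dosing of all team members the intervention compared with past years would differ from the one described. No view is taken here on which treatment rule is right.

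**What to change.** 1. Reconcile the Setting section and sections a), b) and g) on who receives capsules, and state the rule in the administration paragraph so that training staff need not infer it from elsewhere.
2. In section i), item 2, describe the two Aim 2 groups to match the reconciled rule. Say that they are defined by baseline level and how January treatment of baseline-normal athletes is to be understood in the comparison.
3. Add capsules given per athlete to the data lists in sections g), h) and j), so that departures from the rule can be seen.

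The cost is about one sentence in section g), matching text for Aim 2, and one small data item. Staff are already expected to account for every weekly dose, so the record should add little work.
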